Study eligibility criteria included women between 18 - 25 years of age engaged in frequent tanning bed use, which was defined as at least 25 indoor tanning sessions in the past 12 months. Participants were recruited using multiple approaches. Qualtrics Sample Providers emailed study advertisements with links to a brief online eligibility screening survey to members of internet panels and posted online advertisements. The screening survey was programmed to present eligible participants with a brief description of the intervention trial and a question to indicate their interest in receiving an email study invitation. Second, recruitment flyers with study personnel contact information were posted on campus and in classrooms at a large Northeastern University and on internet ads on social media and Craigslist. Most participants (96%) were recruited by Qualtrics.

Study Design and Procedure

The study was a 2-arm randomized controlled trial with planned 1:1 allocation. A study coordinator enrolled participants, administered all procedures, and monitored trial progress. Following screening, the study coordinator sent an invitation email with a link to the online baseline survey, programmed using Qualtrics survey software, and a unique study personal identification number (PIN) for accessing the survey. Each PIN was assigned to a study condition, and we used a random number generator to randomly order the PINs in our study tracking spreadsheet. PINs were assigned to participants in order of our receipt of their screening survey and prior to sending the baseline survey invitation. Participants were asked to provide online informed consent prior to beginning the baseline survey and those who did not were not provided access to the survey. Up to three email reminders were sent to individuals who agreed to participate. Links to the web-based intervention were sent to participants two weeks after completing the baseline survey. A brief intervention evaluation survey was presented immediately after participants completed viewing the intervention. All participants who completed the baseline were invited to complete the follow-up assessment 12 weeks later. Participants assigned to the waitlist control were invited to access the intervention after the follow-up surveys concluded. Participants received a gift card for completing the baseline survey, the intervention

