Primary Outcomes. The primary outcomes of indoor tanning bed use, sunburns, and indoor tanning intentions were assessed at both the baseline and follow-up surveys. Participants were asked to recall the number of indoor tanning sessions they had in the past two months. A similar question format was used to assess the number of sunburns they received in the past two months. Sunburns are a commonly-experienced side-effect of tanning bed use and independent risk factor for skin cancer risk (Stapleton et al., 2013). Our measure did not specify if reported sunburns were a result of indoor tanning so the measure is considered to be a general marker of ultraviolet risk behavior. For tanning intentions, participants indicated how likely they were to use an indoor tanning bed in the next year on a 6-point response scale anchored with 1 = *Extremely unlikely* and 6 = *Extremely likely* (Hillhouse et al., 2008).

Exploratory Outcomes. Interest in changing tanning was assessed using a single item (Would you like to reduce or quit indoor tanning if you could do so easily?) adapted from Sobell and colleagues' (1996) questions about readiness to change drinking behaviors (responses coded as 0 = *no* and 1 = *yes*). Self-efficacy in quitting tanning was assessed using Zeller and colleagues (2006) single item assessing perceived difficulty in quitting tanning (How hard would it be for you to stop using tanning beds/booths? (*Please answer on a scale for 0-10, where 0 is "Not at all hard", 10 is "Extremely hard"*)).

Statistical Analyses Plan

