Acceptability and engagement metrics are described for all participants who completed the intervention evaluation. We compared intervention and control participants on their baseline responses for the primary study outcomes and found evidence of non-equivalence. Specifically, intervention participants reported disproportionately higher rates of lifetime indoor tanning use ($M_{\text{intervention}} = 409.0$, $M_{\text{control}} = 158.5$) and 12-month indoor tanning ($M_{\text{intervention}} = 72.3$, $M_{\text{control}} = 49.0$) compared to control participants. A series of 2 (condition) X 2 (time) mixed-measures analysis of variance (ANOVA) was used to examine differences in study outcomes to control for baseline differences between conditions. Our power calculations indicated that a sample size of 54 participants would allow us to detect a moderately large intervention effect (specifically, 80% power to detect an 8 IT session difference between conditions).

Table 1. Intervention map with the goals and brief descriptions of intervention content.

Goal	Content and Description
Enhance interest and readiness to change	Self-exploration of tanning ambivalence. Participants were encouraged to answer open and close-ended questions in which they described individual patterns of indoor tanning bed use and experiences with tanning. Additional personalized feedback tailored to participant responses encouraged reflection on the balances of pros and cons of indoor tanning.
Bolster commitment to change	Normative beliefs about IT. Participants were asked to estimate the percent of women their age who use IT. Following this exercise, participants were provided with the actual percent of women compared to what they believed to be true.
	Desired motives and values. Tanners were asked questions designed to clarify their most important desired motives or values. Through a series of close-ended questions, participants were then encouraged to think about the good and not-so-good aspects of indoor tanning. Following this exercise, personalized feedback was provided to the participant aligning their personal values with the pros and cons of indoor tanning.

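### The 80% power figure is not tied to a named test; if it refers to a single-time-point comparison, the planned condition-by-time test reaches it only at a correlation of 0.5 or more, and a baseline-adjusted ANCOVA largely removes the shortfall

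*Combined protocol and SAP*

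**What the plan says.** The Statistical Analyses Plan says that "a sample size of 54 participants" would allow the trial to "detect a moderately large intervention effect", and specifies this as "80% power to detect an 8 IT session difference between conditions". It gives no SD, alpha, sidedness, correlation, attrition allowance or named test for the calculation, and does not say whether 54 is the total or per arm.

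The design is a "2-arm randomized controlled trial with planned 1:1 allocation" (Study Design and Procedure). For the tanning outcome, participants "recall the number of indoor tanning sessions they had in the past two months", at both baseline and follow-up (Measures, Primary Outcomes). Outcomes are analysed by a 2 (condition) x 2 (time) mixed ANOVA, chosen to control for baseline differences. The same section reports such differences: mean 12-month sessions were 72.3 in the intervention arm and 49.0 in the control arm. No two-month baseline mean is given.

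**The concern.** With two time points, the condition-by-time test in a mixed ANOVA is a two-sample t-test on change from baseline. Its power depends on the correlation between baseline and follow-up, which the plan does not give. The power sentence describes only a difference between conditions, which can be read as a comparison at follow-up alone. On that reading, the stated power and the planned test can part company.

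The stated effect is also hard to judge. The outcome covers two months, and the only baseline session counts reported cover 12 months or a lifetime. A reader cannot see what share of usual use 8 sessions represents, or how much a non-significant result would say about a smaller reduction.

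**Working it through.** **Inputs from the plan.** 54 participants, 1:1 allocation, 80% power, 8 sessions, a two-month outcome, and 12-month means of 72.3 and 49.0.

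**Assumed, because not stated.** 54 is the total (27 per arm); alpha is 5% two-sided; the SD is the same at both times; the correlation rho is varied; use is spread evenly over the year.

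**1. The plan's own figure.** It cannot be reproduced forwards without an SD. Solving backwards with the noncentral t (27 per arm, 52 df), 80% power needs d = 0.777, so SD = 8/0.777 = 10.3. With a one-sided 5% test, d = 0.69 and SD = 11.7. If 54 is per arm, d = 0.54 and SD = 14.7 (two-sided).

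**2. Power for 8 sessions if 10.3 is the SD at a single time point.**
- Condition-by-time test: SD of change = 10.3 x sqrt(2(1 - rho)).
- ANCOVA: residual SD = 10.3 x sqrt(1 - rho²).
- ANCOVA with imbalance: the gap is (72.3 - 49.0)/6 = 3.88 sessions, or 3.88/10.3 = 0.377 SD. The variance of the treatment effect is multiplied by 1 + (27/2)(0.377²)/52 = 1.037 (51 df). This assumes that the two-month gap matches the 12-month gap.

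| rho | SD of change | Condition-by-time power | Difference detectable at 80% | ANCOVA power | ANCOVA power with imbalance |
|---|---|---|---|---|---|
| 0 | 14.6 | 51% | 11.3 | 80% | 78.5% |
| 0.3 | 12.2 | 66% | 9.5 | 84% | 82% |
| 0.4 | 11.3 | 72% | 8.8 | 86% | 85% |
| 0.5 | 10.3 | 80% | 8.0 | 90% | 89% |
| 0.6 | 9.2 | 88% | 7.2 | 94% | 93% |

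The threshold at 0.5 is algebra: sqrt(2(1 - rho)) is at most 1 only when rho is at least 0.5.

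**3. If the 80% was already computed on change scores.** Then 10.3 is the SD of change, the condition-by-time test has 80% power by construction, and no threshold arises. ANCOVA is still the more precise analysis. The ratio of its residual variance to the change variance is (1 - rho²)/(2(1 - rho)) = (1 + rho)/2, which is below 1 for any rho below 1. With the 1.037 factor it stays below 1 up to rho of about 2/1.037 - 1 = 0.93.

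**4. Size of 8 sessions relative to use.**
- Intervention arm: 72.3/6 = 12.05, and 8/12.05 = 66%.
- Control arm: 49.0/6 = 8.17, and 8/8.17 = 98%.
- Equal-weight mean: 60.65/6 = 10.1, and 8/10.1 = 79%.

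**5. Power for smaller reductions.** At SD 10.3, a 30% reduction from 10.1 (3.03 sessions) has 19% power and a 50% reduction (5.05 sessions) has 42%. These hardly depend on the disputed inputs. Once 80% is granted for 8 sessions, power for a smaller difference is set almost entirely by its ratio to 8. Reading 54 as per arm gives the same 19% and 42%; a one-sided test gives 24% and 47%.

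**The case against.** The strongest objection is that the plan does not say which test was powered. Under randomisation, a difference in change and a difference at follow-up have the same expected value, so the power sentence could describe either. A reader might infer that the stated 80% is miscalculated, or that it belongs to a test the plan does not use. The documents do not support either inference, and the 0.5 threshold is conditional. This objection stands.

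Three further inferences also go too far.
- **That the size label is wrong.** With 54 in total, d is 0.69 to 0.78, so calling the effect moderately large is fair on the standardised scale.
- **That 8 sessions means near-complete cessation.** Only the control-arm figure of 98% suggests that. For the arm that is treated before follow-up, the figure is 66%, and controls may also change over 12 weeks.
- **That ANCOVA guarantees at least 80%.** With an imbalance like the observed one, power is about 78.5% at zero correlation and 78.9% at 0.1.

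The percentages of use rest on dividing a 12-month recall by six. Baselines ran from April to November and follow-ups from July to February, so seasonality could shift them.

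Finally, the trial presents itself as formative and claims only a preliminary look at impact, which limits the harm from a loose power statement. It does not remove the reason to use the more precise analysis, since the baseline count is already in hand.

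**Conclusion.** The point holds in conditional form. The power statement omits the test, SD, alpha and correlation, so it cannot be matched to the planned analysis. If it refers to a single-time-point comparison, power for 8 sessions on the condition-by-time test is 51% to 72% at correlations from 0 to 0.4, and 80% or more only from 0.5 upwards. If it refers to change scores, there is no shortfall.

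On either reading ANCOVA is more precise at any plausible correlation, so the case for it does not depend on settling which test was powered. The low power for 30% and 50% reductions also holds on either reading, given the stated 80% for 8 sessions and even use over the year. A non-significant result would therefore say little about reductions of that size.

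**What to change.** 1. Replace the condition-by-time test for tanning sessions with an ANCOVA of the follow-up two-month count on condition, adjusting for the baseline two-month count. If outcome results have already been seen, record this as a change to the planned analysis and show the condition-by-time result beside it.
2. State the SD, alpha, sidedness, correlation and test behind the 80%, and whether 54 is the total. Tie the figure to the ANCOVA. If the single-time-point reading is right, quote about 84% at correlation 0.3 and 90% at 0.5, with about one point less for the observed imbalance, so roughly 79% near zero correlation.
3. Beside the 8 sessions, give the relative size (about 79% of implied two-month use; 66% and 98% by arm) and the power for 30% and 50% reductions (about 19% and 42%), with the even-use assumption stated. The actual two-month baseline mean, which was collected, would be a better denominator.
4. Report the estimated difference with its 95% interval. The size label may stay if it is described as standardised (d about 0.7 to 0.8).

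The cost is one refitted model on data already collected, one degree of freedom, and a few sentences. No participants or assessments are added.
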